- 1) **Date:** 12/18/23
- 2) **Study Title:** Supplementation with a Next Generation Synbiotic in Individuals with Overweight or Obesity: A Triple-Blinded Randomized Controlled Trial
- 3) **Principal Investigator (must be a TCU faculty or staff):** [name]
- 4) **College/School:** Texas Christian University
- 5) **Other Investigators:** List all faculty, staff, and students conducting the study. For those not affiliated with TCU, please provide their names and institution.
[name], [name], [name], [name], [name], [name], [name], [name], [name], [name], and [name]
- 6) **If you have internal or external funding for this project –**
Funding Agency: The supplement company Pendulum will provide the product (probiotic and placebo with a market value of \$50,400). The Dean's Opportunity Fund will provide \$49,512 for blood analyses, blood and stool sample tubes, and stool sample whole genome sequencing. [name] will provide part of her start up funds (\$6,000) for participants compensation. **Project #: IRB#2023-345** **Date for Funding:** November 2023
- 7) **If you intend to seek/are seeking internal/external funding for this project –**
Funding Agency: TCU Graduate SERC Grant
Amount Requested From Funding Agency: \$2,000
Due Date for Funding Proposal: October 23rd, 2023
- 8) **Purpose: Describe the objectives and hypotheses of the study and what you expect to learn or demonstrate:** Our proposed triple-blinded, placebo controlled, randomized clinical trial is divided into two stages.
The first stage will consist of exploring the effect of next generation synbiotic supplementation for 12 weeks on body composition, insulin sensitivity, gut microbiota composition and diversity, depression, anxiety, and food cravings in 60 individuals with overweight or obesity who have no diagnosis of diabetes mellitus (DM). For this first stage, we hypothesize that this next generation synbiotic will decrease adiposity, overall body weight, anxiety, depression, and food cravings and increase insulin sensitivity, and gut microbiota diversity. We also hypothesize that the levels of bacterial species in the symbiotic will increase in the gut microbiome.

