The second stage will only be conducted if enough external funds are ensured by using the results from the first stage as preliminary data. The second stage would consist of performing 16S rRNA on blood samples to analyze microbial composition in blood, and metabolomic analysis to evaluate the effect of the probiotic on gut-derived metabolites in blood and stools. The hypothesis of this second stage of the project is that the next generation symbiotic will change blood microbial composition as well as the presence and concentration of gut-derived metabolites in blood and stool samples. If relationships exists between changes in body composition, insulin sensitivity, depression, anxiety, or cravings (first stage variables) with blood microbial composition and derived-

metabolites (second stage variables), we could show not only a cause-effect relationship but also the mechanism of action through which the next generation symbiotic acts.

9) Background: Describe the theory or data supporting the objectives of the study and include a bibliography of key references as applicable.

Obesity is a strong risk factor for the development of the majority of the leading causes of death.¹ Recent research has pointed to the gut microbiota as a potential mechanism of action through which body weight can be regulated.² The gut microbiota of people with obesity has a lower alpha diversity³ and lower abundance of *Akkermansia muciniphila*.⁴⁻⁷

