The triple blinding nature of this study means that participants, researchers (including the PI), and statisticians cannot be made aware of the randomization allocation. Therefore, debriefing to participants can only take part until after data has been analyzed. Once all participants have finalized their interventions and all data has been analyzed, researchers will contact back participants to verbally give them the debriefing statement and inform them which supplement/placebo they received.

14) Study Procedures: Provide a chronological description of the procedures, tests, and interventions that will be implemented during the course of the study. Indicate the number of visits, length of each visit, and the time it would take to undergo the various tests, procedures, and interventions. If blood or tissue is to be collected, indicate exactly how much in volume and all procedures that will be done with collected samples. Describe when, where and how collection will take place. Flow diagrams may be used to clarify complex projects. For Non-TCU study team members please explain their study team role in detail. If the study involved deception justify the use of deception and explain why deception is necessary to achieve the goals of the study. Explain if alternative methods not involving use of deception were considered and why these methods are not being used.

STAGE 1

For stage 1, participants will come to TCU on three days total:

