In the first visit, participants will come for 45 minutes to the Rickel Department where they will receive a complete explanation of the protocol and will process to sign the "Informed Consent to Participate in Research and Authorization to Collect, Use, and Share their Health Information" if agreeing to participate. Participants' height and weight will be measured to ensure they meet BMI inclusion criteria. Height will be measured using a standard stadiometer and weight will be measured using a standard calibrated digital scale. Their race will be asked to help in data interpretation. Height, weight, race and other information relevant to antibiotic prescription such as date of birth, allergies to medications, and preferred pharmacy will be collected at this time point using our document titled "checklist 2". All symbiotic and placebo bottles will be entirely similar with exemption of individual codes that will vary every 3 bottles. This is because each participant will be provided at the beginning of the study with 3 bottles (with similar code) to ensure enough supply for the 12-week supplement intervention. The company Pendulum will perform an *a priori* randomization of the entire study by using blocked randomization with randomly selected blocked sizes with the intention to reduce bias and ensure balance between groups. This randomization will be added into an Excel document in which they will specify the order of the participant in column 1 (example: Participant 001, Participant 002), the code of the bottles in column 2, and the interpretation of the code (placebo vs probiotic) in column 3. A researcher, independent from this study ([name]), will save in different protected locations (Box, secured laptop, protected USB) the randomization document. [name] will share with [name] an Excel document containing column 1 and column 2 of the provided document (the order of participant and the code of the bottles, without the interpretation of each code). [name] will use the supplement code as the participants' IDs and study data will be added to this Excel document. Both documents, from, [name] and from [name], will be merged at the end of the study, once data has been analyzed to figure out the intervention group to which each participant belonged. During the first

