visit, depending on the order they enrolled, participants will receive the 3 bottles containing the assigned code. Participants will also be provided with two stool sample collection kits, a 3-day diet record form, a 3-day prescription of antibiotics (500 mg of generic Vancomycin every 8h), date for second appointment, and a start date for the antibiotic regimen. The 3-day antibiotic treatment provided prior to beginning the 12-week synbiotic intervention is given with the intention to increase the number of available bacterial niches (bacterial homes/space) and thus increase the engraftment of the newly ingested bacteria. Although participants will be asked to pay the cost of the generic antibiotic treatment initially (which should have an estimated cost of \$20-25), we will offset the cost of the antibiotic by providing the participants with a \$50 Amazon gift card in their second appointment, so they will not be responsible for any costs to participate in this study. This initial gift card is in addition to their \$100 Amazon gift card provided at the end of the study in appreciation for having taken part in this project. Their insurance will not be charged for any study-related testing; however, they are welcome to (but don't have to) use their insurance to buy the antibiotic. During this first visit, participants will have their 1) first 12h fasted blood collection and will be instructed to 2) fill out a 3 day food log before each stool sample collection, 3) collect a stool sample before the start of the antibiotic regimen, 4) collect a stool sample within 12-48 hours after the last dose of the antibiotic regimen, 5) bring both stool samples and diet records with them to the second appointment and, 6) fast 12 hours prior to the second appointment (refrain from the consumption of all food and liquids, except water). The first appointment is expected to take no greater than 45 minutes.

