- 1) There are a total of 2 DEXA scans in this study. This will expose participants to low-dose radiation, the amount of radiation exposure is small and is about the same as one day of normal background radiation per scan. Exposure to ionizing radiation at low levels has the potential of causing cancer later in life. The risk of this occurring increases as the amount of exposure increases. The amount of radiation exposure in this study is very small and so the additional risk of causing radiation related effects does not change significantly by participating in this study. Prior to any body composition measurements, participants who are female and of childbearing age will be required to complete a pregnancy questionnaire. To minimize the radiation-related risks, females who become pregnant will be unenrolled from the study and will not undergo DEXA scanning. While radiation exposure is low, the consent form includes a statement that instructs participants to let the researchers know if they are in any other studies involving DXA scans in order to consider cumulative radiation exposure.
- 2) Although the antibiotic intervention is short (3 days) and might not be enough to cause gastrointestinal discomfort is possible that susceptible people may still experience gastrointestinal symptoms such as bloating and diarrhea. Secondary infections to antibiotic treatment, such as *Clostridioides difficile*, although unlikely are also possible. Short antibiotic interventions, however, cause minimal microbiota changes that are temporary and reversible (DOI: 10.1016/j.cell.2018.08.047). The antibiotic and dose chosen in this trial were the most highly used according to a systematic review our team published in 2022 in which we compared RCTs evaluating the effect of "antibiotic" versus "antibiotic + probiotics" (DOI: 10.1099/jmm.0.001625). Gastrointestinal discomfort at such short antibiotic interventions is unlikely, however, if present, symptoms tend to subside within a short period of time.
- 3) Likewise, supplementation with live bacteria strains (probiotics) and/or prebiotics may induce gastrointestinal discomfort secondary to microbiota composition changes.

- 4) Individual verbal treatment debriefing (placebo vs symbiotic) will take place after participant recruitment and data analysis have finalized as this is the time point in which we will reveal the randomization process.

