If participants withdraw from their study the data collected up to that point will remain available for research purposes with the intention to use intent to treat analysis. Blood and stool samples will be stored in [name] lab located within the Rickel building room 259. For the first stage of the project, blood samples will be analyzed at [name] lab room 259. Once the Nutritional Sciences Department laboratory has been finalized, samples will be transferred to the Nutritional Sciences Department and further storage and analyses could take place here (BASS, room 1203). If enough funds become available to perform the second stage of the study, blood and stool samples (which will be identified by fabricated ID) will be sent to Baylor College of Medicine and to Metabolon for posterior 16S rRNA/WMS and mass spectrometry analyses, respectively. For statistical analysis of the first stage, two sample T-tests will be used to compare within (pre- versus post- values on each group) and between-group (placebo versus probiotic) differences in body composition, adherence, metabolic, dietary, and psychological variables. SPSS will be used for statistical analysis. A p value <0.05 will be considered as statistically significant. Dietetic variables collected via the NCI Automated Self-Administered 24-hour Dietary Assessment Tool including protein, carbohydrate, fat, and fiber will be controlled statistically in the case that significant intra-individual or between-group differences are observed.

20) Check List for the Items That Need to be Submitted: Please submit protocol and consent documents separately in MS word, supplemental documents (interview guides, surveys, recruitment materials etc. can be submitted as separate pdfs) before submitting the materials electronically to the IRB. To prevent any delay in the approval of your protocol, use the most recent template for the protocol, consent document, and HIPAA form by downloading them from <https://research.tcu.edu/research-compliance/irb/irb-forms-templates/> each time you prepare your materials.

a. Protocol	X
b. Consent document	X
c. Protecting Human Research Participants Training complete for each investigator	X
d. Recruitment flyers, letters, ads, etc.	X
e. Questionnaires or other documents utilized in screening and data collection	X

Principal Investigator Assurance

21) By signing below, I certify to the following:

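### Section 19 calls any within-arm or between-arm t-test with p<0.05 significant and names no primary outcome; across six hypotheses the chance of a false between-group result favouring the synbiotic is about 8% to 14%, against 2.5% for one test

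*Combined protocol and SAP*

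**What the plan says.** Section 19 (Data Analyses) holds the whole stage 1 statistical plan. It states that "two sample T-tests will be used to compare within (pre- versus post- values on each group) and between-group (placebo versus probiotic) differences" in variables covering body composition, adherence, metabolism, diet and psychology. The threshold follows: "A p value <0.05 will be considered as statistically significant". It does not say whether tests are one-sided or two-sided.

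Section 8 (Purpose) describes stage 1 as exploring effects in 60 participants, then hypothesises that "this next generation synbiotic will decrease adiposity, overall body weight, anxiety, depression, and food cravings and increase insulin sensitivity, and gut microbiota diversity". That makes seven directional hypotheses. The next sentence adds an eighth, that the supplemented species will increase in the gut. All eight have equal rank.

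Section 14 (Study Procedures, second visit) lists several measures for some hypotheses. For adiposity there are DEXA fat mass, DEXA visceral fat and BOD POD fat percentage. On the metabolic side there are fasting glucose, fasting insulin and HbA1c. The section does not say which measure decides.

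No section names a primary outcome, orders the tests, adjusts for multiplicity, or gives a power calculation from which a primary outcome could be inferred.

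**The concern.** With equal-rank outcomes and one unadjusted threshold, a statement that the synbiotic works could rest on whichever between-group test crosses 0.05. The more outcomes are tested, the likelier it is that one does so by chance. The reader of the eventual report could not tell a planned finding from a selected one.

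The within-arm tests raise a different problem. A significant change from before to after in the synbiotic arm uses no information from the placebo arm. It may reflect anything that happens to all participants over 12 weeks. A significant change in one arm and a non-significant change in the other is not a test of the difference between arms. Section 19 nevertheless gives both kinds of result the same standing.

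**Working it through.** The document states no error rate for the set of tests, so there is no figure of the plan's own to reproduce.

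**Inputs from the document**
- Threshold per test: 0.05 (section 19).
- Directional hypotheses: 8 (section 8). Six belong to the kinds of variable that section 19 assigns to t-tests: adiposity, body weight, anxiety, depression, food cravings and insulin sensitivity. Microbiota diversity and species levels are not in that sentence and are left out.

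**Assumptions, not given in the document**
- No true effect on any of the six.
- Two-sided tests, so each has a chance of 0.025 of falsely favouring the synbiotic.
- One between-group test per hypothesis.
- Outcomes aligned so that higher is better, with a common correlation ρ between test statistics.

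**Formulas**
- Independent tests: P = 1 − 0.975^6 = 1 − 0.859 = 0.141.
- Common correlation: P = 1 − ∫ φ(u) · Φ((1.96 − √ρ·u)/√(1−ρ))^6 du, integrated numerically.

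| Correlation ρ | Chance of at least one false result favouring the synbiotic |
|---|---|
| 0 | 14.1% |
| 0.3 | 12.2% |
| 0.5 | 10.4% |
| 0.7 | 8.2% |
| 0.8 | 6.9% |
| 0.9 | 5.4% |
| Single test | 2.5% |

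**Checks**
- Simulated t-tests with 30 per arm (an equal split of the 60, also assumed) gave 13.9%, 12.2%, 10.4% and 8.1% at correlations 0, 0.3, 0.5 and 0.7.
- A more realistic pattern, with correlations of 0.8 to 0.9 between the two body-composition outcomes and 0.5 to 0.7 among the psychological ones, gave 9.9% to 11.7%.
- In either direction, six independent tests give 1 − 0.95^6 = 26.5%, against 5% for one.

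**What is left out.** Testing several measures for one hypothesis would raise these figures. So would counting the within-arm tests as evidence for the synbiotic.

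**Within-arm tests.** No arithmetic is needed. Randomisation makes the two arms comparable with each other. It does not make an arm after 12 weeks comparable with itself before, so a pre/post p-value cannot isolate the effect of the synbiotic.

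**The case against.** The strongest reply is that stage 1 is exploratory. Section 8 describes it as exploring, and its results are meant to support a later funding application. Unadjusted reporting is defensible in hypothesis-generating work, and section 19 nowhere says that one significant outcome is enough to declare success. This softens the consequence. It does not remove it, because the same section 8 states directional hypotheses and section 19 declares significance without an exploratory label.

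A reader might infer more than the document supports, in four ways.

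- **That stage 1 t-tests will be used to claim causation.** Section 8 does say "we could show not only a cause-effect relationship", but that sentence depends on associations with stage 2 variables, and stage 2 depends on funding.
- **That 8% to 14% is the error rate of the whole plan.** It counts six between-group tests only. Section 19 also covers within-arm tests and adherence and dietary variables. Counting every DEXA output as a possible success would not be fair either, because section 8 states no hypothesis for lean mass or bone density.
- **That a definite false-lead rate can be attached to the within-arm tests.** Section 19 calls them two-sample tests. Whether a paired or an unpaired test is run, the pre/post correlation and the size of any change shared by both arms would all drive the figure. The document gives none of the last two, and its wording on the first does not fit a paired test.
- **That the antibiotic will produce such a shared change.** Section 14 describes "The 3-day antibiotic treatment provided prior to beginning the 12-week synbiotic intervention", prescribed to all participants. Section 15 says that short courses have small and reversible effects on the microbiota, and no section says that they alter weight, fat mass or mood. The within-arm point does not need this mechanism.

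It is also fair to say that the lower end of the range depends on where the correlation is cut off. At 0.8 the figure is 6.9%, still nearly three times 2.5%.

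**Conclusion.** The concern holds in a limited form. Section 19 gives equal significance status to every within-arm and between-arm t-test, and nothing in the document singles out a primary comparison. For the six hypotheses under these tests, the chance of at least one false between-group result in favour of the synbiotic is several times that of a single test. The size rests on two-sided testing, no true effect, one test per hypothesis and an assumed correlation. The missing primary outcome does not rest on any of these. The within-arm point stands on design grounds alone. Neither point shows that the trial will make an unsound claim; they show that the plan as written would allow one.

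**What to change.** Amend section 19 before any outcome data are examined. Setting the limit at unblinding would not be enough, because the document places the reveal after the analysis: section 13 says that "debriefing to participants can only take part until after data has been analyzed", section 14 says that the allocation files "will be merged at the end of the study, once data has been analyzed", and section 15, having placed debriefing after data analysis, says that "this is the time point in which we will reveal the randomization process".

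1. Name one primary outcome, chosen by the investigators, and one between-group comparison at two-sided 0.05. The false favourable rate for that claim is then 2.5%. Alternatively, state that all stage 1 outcomes are exploratory.
2. Base any claim about the synbiotic on between-group comparisons only. Report within-arm changes and all other outcomes as estimates with confidence intervals and no significance claim.
3. If confirmatory secondary claims are wanted, pre-specify a short list tested by Holm at 0.05 only if the primary is significant. Without that gate, two families at 0.05 each could reach a combined two-sided error of up to 0.05 + 0.05 = 10%.

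If outcome data have already been examined, say so and label every outcome exploratory.

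The cost is one paragraph, with no new data or visits. The downside is that fewer outcomes can be called significant, and a real effect on a non-primary outcome might be reported only as exploratory.

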Synbiotics combine probiotics (alive bacteria) and prebiotics (bacteria food) in order to improve microorganism survival and activity within the host.²³ The synbiotic that will be used in this trial contains the oligosaccharide-degrading probiotics, *A. muciniphila* and *Bifidobacterium infantis*; butyrate producers such as *Clostridium beijerinckii*, *Anaerobutyricum hallii*, and *Clostridium butyricum*; and chicory-derived inulin, a prebiotic dietary fiber. Butyrate is a gut-derived short chain fatty acid suspected to play a role in weight regulation and insulin resistance.²⁴ Butyrate administration in mice models of obesity improves weight and fat mass regulation, increases lipid oxidation in brown adipose and liver tissue, and stimulates the production of gut-derived neuropeptides involved in energy homeostasis and food intake, such as GIP, GLP-1, PYY, and serotonin, and decreases fasting insulin.²⁵⁻²⁷ A previous pilot clinical trial indicated the synbiotic that will be used in the current study to be safe and tolerable as well as effective in reducing HbA1c and improving post-prandial glucose control in individuals with type 2 diabetes mellitus (T2DM) and overweight or obesity,²⁸ however, no studies have analyzed the effect of the synbiotic on body composition, anxiety, and depression in individuals with overweight who do not have T2DM.

References:

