For the second visit, participants will meet researchers at the Rickel building. This appointment is expected to take approximately 45 minutes and includes the completion of a DEXA scan, an air displacement plethysmography test (via BOD POD), body weight measurement, the Beck Anxiety and Depression Inventories, the RED-9 questionnaire, and a blood draw. Participants will turn in their first (before antibiotic prescription initiation) and second (after antibiotic prescription completion) stool samples and food logs to researchers. The blood draw will consist on 2 serum separation tubes (10 mL each), 1 EDTA tube (3 mL), and 1 Zymo tube (3 mL). The time to complete each test is approximately as follows: 10 minutes for the blood draw, 10 minutes for the anxiety and depression survey, 20 minutes for the DEXA scan, and 5 minutes for an air displacement plethysmography test. Air displacement plethysmography tests via the BOD POD will be used to measure body fat percentage. Participants will be asked to wear minimal clothes and no shoes for the air displacement plethysmography test. The DEXA scans will be used to measure fat mass, visceral fat, lean mass, and bone mineral density. The DEXA scan uses a two-sided low emission X-ray to quantify lean body mass, fat mass, and bone density. To conduct the test, participants will be asked to void their bladder, remove all metal objects (piercings, rings, etc.) and shoes, and will lay supine on a padded table for approximately 6 minutes while the scanner moves down the length of the participant's body. Measurements will be conducted by a General Electric Certified DEXA Operator ([name] or [name]). Blood samples will be collected using sterile techniques and only by qualified investigators ([name] or [name]). Blood samples will be used to measure fasting glucose, fasting insulin, and HbA1C. Blood will be sampled using venipuncture. The venipuncture samples will be collected using a traditional blood draw needle to extract blood from a vein in the antecubital region of the arm. Two 10 mL vials of blood will be collected, centrifuged to separate the serum. One of those tubes will be stored in a -80°C freezer in the Exercise Physiology Laboratory (Rickel 259) whereas the other will be transported to BioReference for fasting glucose and insulin analysis. The 3 mL for EDTA analysis will also be transported to BioReference for HbA1C analysis. The Zymo collection tube (3 mL) will be stored at the Rickel 259 building. All blood collection vials and plasma/serum containers will be

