
labeled using participant numbers (deidentified) for participant privacy. The leftover blood samples will be stored in the laboratory for 10 years from date of collection at which point they will be discarded as biohazard waste. Participants agree to allow their deidentified samples to be used for future research by signing the informed consent. These procedures have been approved by the TCU Institutional Biosafety Committee (IBC Protocol). At the end of the second appointment, participants will be provided with the 12 weeks of the probiotic+prebiotic supplement. Each person will receive 3 bottles (one per month) with the three of them having the same ID, this same ID will be used to identify all questionnaires and samples obtained from that person. This ID will also be different between each participant. Participants will also be instructed to 1) record everything they eat for 72 hours before stool sample collection, 2) collect a stool sample within 24 hours of finishing the last dose of the intervention, 3) bring the stool sample, diet record, and remnant of their supplement or placebo with them to the third appointment, and 4) fast 12 hours prior to the third appointment (refrain from the consumption of all food and liquids, except water).

The third and final appointment is expected to also take approximately 45 minutes and will include a replication of all tests conducted in the second appointment (completion of a DEXA scan, an air displacement plethysmography test [via BOD POD], body weight measurement, the Beck Anxiety and Depression Inventories, the RED-9 questionnaire, and a blood draw [consisting on 2 serum separation tubes of 10 mL each, 1 EDTA tube of 3.5 mL, and 1 Zymo tube of 3mL]). Participants will turn in their third and final stool sample, as well as the remnant of their supplements or placebo for analysis of adherence and compliance. Participants will receive a \$100 Amazon gift card at the end of the study in compensation for their time. After all stool samples have been collected, they will be sent in the same batch to the Alkek Center for Metagenomics and Microbiome Research (CMMR) at Baylor College of Medicine in Houston for posterior whole genome sequencing analysis.

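### The diet-adjustment rule is not limited to diet recorded before the product, so the placebo-versus-synbiotic comparison may be adjusted for diet that the product itself may have changed

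*Combined protocol and SAP*

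**What the plan says.** Section 19 names four nutrients and says that they "will be controlled statistically in the case that significant intra-individual or between-group differences are observed". It does not say which diet record is meant, which model would be used, or whether an adjusted result replaces or accompanies the t-test. Significance is set at p<0.05.

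Diet is also analysed in its own right. The section states that "two sample T-tests will be used to compare within (pre- versus post- values on each group", and adds the placebo-versus-probiotic comparison. Both are applied to "differences in body composition, adherence, metabolic, dietary, and psychological variables".

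Section 14 (Study Procedures) sets out three food records. At the first visit participants are told to "fill out a 3 day food log before each stool sample collection". There are two such samples before the second visit: one before the antibiotic, and one for which they must "collect a stool sample within 12-48 hours after the last dose of the antibiotic regimen". At the second visit, "Participants will turn in their first (before antibiotic prescription initiation) and second (after antibiotic prescription completion) stool samples and food logs to researchers". For the third visit they are told to "record everything they eat for 72 hours before stool sample collection", and that sample is due within a day of the last dose of the 12-week product.

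Section 8 (Purpose) hypothesises that the synbiotic lowers food cravings. Section 9 (Background) reports that in mouse models butyrate "stimulates the production of gut-derived neuropeptides involved in energy homeostasis and food intake", and says that the product contains butyrate producers. No hypothesis is stated on intake itself.

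**The concern.** Randomisation makes the arms comparable in diet before the product is taken. A difference in diet between arms at the end of the product period may therefore be an effect of the product. The plan treats such a difference as a nuisance to be controlled, although it also lists diet among the variables compared by group.

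Three things are at stake. If the product changes eating and eating changes body composition or glucose measures, adjusting for end-of-product diet removes that part of the effect. If diet and outcome share unmeasured causes, the adjustment can bias the estimate in either direction. And because a p-value decides whether to adjust, the data choose between two different target effects.

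**Working it through.** **Inputs.** From the documents: 60 participants (section 11), blocked randomisation with no ratio stated (section 14), p<0.05 and four nutrients (section 19), and the food-record timings above. Assumed: 30 per arm, two-sided tests, and every effect size. The plan gives no power, SD or effect figure, so there is nothing of its own to reproduce.

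**Step 1: which records can the rule reach?** Of the three records, only the last follows the product period. A placebo-versus-probiotic test on diet with no time point includes that record. Nothing in section 19 confines the between-group trigger to baseline.

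**Step 2: what does adjustment estimate?** Let T be the arm, M end-of-product intake and Y the outcome, with M and Y having within-arm SD 1:
- M = a·T + e_m
- Y = (τ − a·b)·T + b·M + e_y

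Here τ is the total effect, a the intake shift and b the slope of outcome on intake. The unadjusted difference targets τ. The M-adjusted difference targets τ − a·b. If instead b = 0 and the residuals have correlation ρ, it targets τ − a·ρ. With τ = 0.70:
- a = 0.3, b = 0.2: 0.70 − 0.06 = 0.64
- a = 0.3, b = 0.5: 0.70 − 0.15 = 0.55
- a = 0.5, b = 0.5: 0.70 − 0.25 = 0.45
- a = 0.3, ρ = ±0.3: 0.70 ∓ 0.09 = 0.61 or 0.79
- a = 0.5, ρ = ±0.3: 0.70 ∓ 0.15 = 0.55 or 0.85

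**Step 3: what does the trigger do?** With 30 per arm, the between-group diet test is significant when the observed difference exceeds about 2.00 × √(2/30) = 0.52 SD. In simulation (40,000 trials per setting, one nutrient, ANCOVA on M if triggered, otherwise the t-test) it fires in 5%, 21% and 48% of trials at a = 0, 0.3 and 0.5. Unadjusted power at 0.70 SD is 76%.

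| Assumed setting, τ = 0.70 SD | Always adjusted | Between-group trigger: mean estimate, power | Within-person trigger added |
|---|---|---|---|
| no shift | 0.70 | 0.70, 75–77% | no bias |
| a = 0.3, b = 0.2 | 0.64 | 0.67, 72% | 0.67, 72% |
| a = 0.3, b = 0.5 | 0.55 | 0.63, 70% | 0.62, 69% |
| a = 0.5, b = 0.5 | 0.45 | 0.53, 56% | 0.50, 52% |
| a = 0.3, b = 0, ρ = +0.3 / −0.3 | 0.61 / 0.79 | 0.66 / 0.74 | not needed |
| a = 0.5, b = 0, ρ = +0.3 / −0.3 | 0.55 / 0.85 | 0.60 / 0.80 | not needed |

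The last column uses the two-sample pre/post test that the plan names, with a pre/post intake correlation of 0.5 (assumed).

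Consistency check: the mean under the rule is τ − P(trigger) × b × (mean observed diet difference when triggered). For a = b = 0.5, 0.70 − 0.53 = 0.17 = 0.48 × 0.5 × 0.71. A mean of 0.71 SD is plausible for differences that usually had to exceed 0.52.

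With diet-record reliability of 0.5, the three mediated rows become 0.69, 0.67 and 0.63 SD under the between-group trigger.

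With no true effect and shared causes, type I error is 4.8% at no shift and 5.0–5.2% at a = 0.3. At a = 0.5 it is about 6.8% for the between-group trigger and 7.6–7.7% with the within-person trigger added.

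**Step 4: more than one nutrient.** Even with no product effect, four independent between-group tests give at least one p<0.05 with probability 1 − 0.95⁴ = 18.5%. That causes no bias, but chance then chooses the analysis.

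**Step 5: which log can serve as baseline?** If the second log ends at its stool sample, 72 h minus 12–48 h leaves 24–60 of its hours within the antibiotic course. Section 14 also hands out the bottles at the first visit in one place and at the end of the second visit in another. The second log therefore cannot be confirmed as pre-product. The pre-antibiotic log precedes the product on either account.

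**The case against.** The wording allows milder readings, and a fair critic would press five points.

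- **Parallel triggers.** Section 19 has two kinds of test and two kinds of trigger. The within-person trigger may govern only the within-group tests. This stands, so the point rests on the between-group trigger, and the last table column holds only if both triggers feed the treatment comparison.
- **Supplementary use.** Adjusted results may only accompany the t-tests. The text does not exclude this, nor does it say so.
- **Baseline imbalance.** The between-group trigger may have been meant for pre-product diet. That is possible, but no words restrict it, and diet is compared by group without a time point.
- **Instrument.** Section 19 names a self-administered 24-hour recall tool, while section 14 describes 3-day or 72-hour records. That these are the same data is an inference.
- **Size.** All magnitudes are assumed. At a 0.3 SD shift they are modest, and noisy records shrink them. The first stage is described as exploring effects. This limits how strongly the consequence can be put, but does not make the rule sound.

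A reader might infer that the plan will adjust the treatment effect for on-product diet, or that the product is known to change intake. The documents support neither. They permit such adjustment, and they make a change in eating plausible through the cravings hypothesis and the mouse mechanism.

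**Conclusion.** The point holds in this form: the rule has no time limit, and its between-group trigger alone permits the treatment comparison to be conditioned on end-of-product diet. That is clear from the text. Whether it does harm depends on whether the product shifts intake, which the documents do not show.

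Without a shift there is no bias. With a shift of 0.3 to 0.5 SD and the assumptions above, a 0.70 SD effect is estimated on average at 0.53 to 0.80 SD under the between-group trigger. In the mediated case it falls to 0.50 SD if the within-person trigger also counts. These figures are illustrations for one nutrient, not predictions for this trial.

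It should be fixed, because the rule could alter any of the treatment comparisons and the remedy is cheap.

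**What to change.** Delete the significance-triggered rule from section 19 and put in its place, for example:

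> Between-group comparisons of outcomes will not be adjusted for diet recorded after the product is started. End-of-product diet will be reported as an outcome by group. Any analysis, between or within groups, that adjusts for it is exploratory.

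If diet adjustment is wanted, prespecify the pre-antibiotic food log as a covariate in a named model such as ANCOVA, and include it whatever its p-value.

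Two sets of passages also need reconciling: the places in section 14 that say when bottles are handed out, and the diet instrument in section 19 against the food records in section 14. Until the first is settled, the second food log should not be treated as pre-product.

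The cost is a few sentences and no new data. The analysts lose a little flexibility, and the comparison at equal diet becomes exploratory.
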